- 6. History or presence of gastrointestinal (including prior bariatric bypass surgery), hepatic (including alanine aminotransferase [ALT] or aspartate aminotransferase [AST] ≥ 2 x upper limit of normal [ULN] or total bilirubin ≥ 1.5 ULN), or severe renal impairment or end-stage renal disease, or any other condition that, in the opinion of the investigator, may interfere with absorption, distribution, metabolism, or excretion of drugs. Participants with hyperbilirubinemia who have a history of Gilbert's syndrome may be eligible for the study; participants whose screening laboratory test results demonstrate predominantly unconjugated hyperbilirubinemia must be evaluated to exclude other diagnoses and, subsequently, must have the diagnosis of Gilbert's syndrome established in order to be eligible.
- 7. Presence of significant cardiovascular disease at Screening including but not limited to the following:
 - a. Myocardial infarction within the past year;
 - b. Unstable angina pectoris;
 - c. Symptomatic congestive heart failure (American College of Cardiology/American Heart Association stage C or D);
 - d. Revascularization procedures within the past year;
 - e. Ventricular cardiac arrhythmias requiring automatic implantable cardioverter defibrillator or medication therapy;
 - f. Uncontrolled hypertension, or systolic blood pressure ≥ 155 mmHg or diastolic blood pressure ≥ 95 mmHg (based on the average of triplicate assessments at Screening Visit 1, Screening Visit 2, or Baseline);
 - g. Clinically significant ECG abnormality per the investigator assessment, or Fridericia's corrected QT interval (QTcF) > 450 msec for men and > 470 msec for women, based on the average of triplicate assessments at Screening or Baseline; or

- h. Any history of cardiovascular disease or any significant cardiovascular condition that in the investigator's opinion may jeopardize participant safety in the study
- 8. History or presence of bipolar and related disorders, schizophrenia, schizophrenia spectrum disorders, or other psychotic disorders according to the Diagnostic and Statistical Manual of Mental Disorders, 5th edition (DSM-5) criteria.

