APPENDIX 3. CLINICAL LABORATORY TESTS

The tests detailed in Table 6 will be performed by the central laboratory, with the exception of urine pregnancy and breath alcohol tests, which will be performed locally. Breathalyzers and urine pregnancy tests will be provided by the central laboratory.

Protocol-specific requirements for inclusion or exclusion of participants are detailed in Section 5 of the protocol.

Additional tests may be performed at any time during the study as determined necessary by the investigator or required by local regulations.

Investigators must document their review of each laboratory safety report.

Table 6: Protocol-required Safety Laboratory Tests

T 1 4 T 4	D					
Laboratory Tests	Parameters					
Hematology	Platelet Count	RBC Indices:			WBC count with Differential:	
	RBC Count	MCV	Neutr Lymp			
	Hemoglobin	MCH			*	
	Hematocrit	%Reticulocytes			ocytes	
				l	nophils	
				l .	phils	
Clinical	Albumin	ALP	ALT/ SGPT		AST/ SGOT	
Chemistry ^a	BUN	Calcium	CO ₂		Chloride	
	Creatinine	Creatine kinase	GGT		Glucose	
	Lactate dehydrogenase	Phosphorus	Potassium		Prolactin	
	Sodium	Total and direct bilirubin	Total cholest	erol	Total protein	
	Triglycerides	Uric acid	INR		eGFR ^b	
Routine Urinalysis	 Appearance, color Specific gravity pH, glucose, protein, occult blood, ketones, bilirubin, urobilinogen, nitrite, and leukocytes (by dipstick) Microscopic examination (if blood or protein is abnormal) 					
Pregnancy testing	 Highly sensitive serum or urine hCG pregnancy test (as needed for women of childbearing potential)^c Serum pregnancy testing is mandatory at screening, and urine is collected thereafter (unless serum is required by local regulations). 					
Other Tests	Urine drug screen (to include at minimum: amphetamines, methadone, MDMA, barbiturates, benzodiazepines, cannabinoids, cocaine, opiates, and phencyclidine)					

Protocol JZP385-201-04 Amendment 04

Laboratory Tests	Parameters
	Breath alcohol test
	 All study-required laboratory tests will be performed by a central laboratory, with the exception of urine pregnancy and breath alcohol tests

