Abbreviations: ALP = alkaline phosphatase; ALT = alanine aminotransferase; AST = aspartate aminotransferase; BUN = blood urea nitrogen; eGFR = estimated glomerular filtration rate; GGT = gamma-glutamyl transferase; hCG = human chorionic gonadotropin; INR = international normalized ratio; MCH = mean corpuscular hemoglobin; MCV = mean corpuscular volume; MDMA = 3, 4,-methylenedioxymethamphetamine; MDRD = Modification of Diet in Renal Disease; RBC = red blood cell; SGOT = serum glutamic-oxaloacetic transaminase; SGPT = serum glutamic-pyruvic transaminase; WBC = white blood cell.

- ^a All events of ALT or AST \geq 3 × upper limit of normal (ULN) and total bilirubin \geq 2 × ULN (> 35% direct bilirubin) or ALT or AST \geq 3 × ULN and INR > 1.5 which may indicate severe liver injury (possible Hy's Law), must be reported to the sponsor in an expedited manner (excluding studies of hepatic impairment or cirrhosis).
- ^b Calculated via central laboratory using the MDRD method.
- ^c Local urine testing will be standard for the protocol unless serum testing is required by local regulation or IRB/IEC. Serum pregnancy testing for confirmation of positive urine test, as well as locally or IRB/IEC required serum testing will be performed at the central laboratory. Serum pregnancy testing is mandatory at screening, and urine is collected thereafter.

Protocol JZP385-201-04 Amendment 04

APPENDIX 4. ADVERSE EVENTS AND SERIOUS ADVERSE EVENTS: DEFINITIONS AND PROCEDURES FOR RECORDING, EVALUATING, FOLLOW-UP, AND REPORTING

Definition of AE

AE Definition

- An AE is any untoward medical occurrence in a clinical study participant, temporally associated with the use of study intervention, whether or not considered related to the study intervention.
- Note: An AE can therefore be any unfavorable and unintended sign (including an abnormal laboratory finding), symptom, or disease (new or exacerbated) temporally associated with the use of study intervention.

Events Meeting the AE Definition

- Any abnormal laboratory test results (hematology, clinical chemistry, or urinalysis)
 or other safety assessments (eg, ECG, radiological scans, vital signs
 measurements), including those that worsen from baseline, considered clinically
 significant in the medical and scientific judgment of the investigator (ie, not related
 to progression of underlying disease).

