7.6. Changes to Planned Analyses

Section 9.4.1.4 of the Protocol outlines the approach to imputation of missing item scores, as part of the TETRAS composite outcome score. Based on these rules, it was possible for a participant to have a missing TETRAS PS score at a visit and still have a valid composite outcome score. The rules have been amended to change the imputation of missing item scores to be managed within the individual subscale scores (ADL or PS) before the composite outcome score is calculated. The details of the new calculation are specified in Section 7.2.5.

The mITT Analysis Set defined in the Protocol Section 9.3 has been updated to ITT, to include all randomized participants for the primary efficacy analyses.

For Adverse Events of Special Interests defined in Protocol Section 8.4.6, presyncope was removed in the formal definition of AEOSI in Section 10.2.1.

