10.3. Laboratory Assessments

The continuous clinical laboratory assessments (hematology, chemistry, and urinalysis) will be summarized at each visit using descriptive statistics. The change from Baseline will be provided at the Week 12.

Shift tables will summarize changes in clinical laboratory assessments at each of the post-baseline visit with respect to baseline. Lab values are categorized into L1, low, normal, high, or H1 based on the lab reference range. L1 and H1 values are predefined per the lab vendor alert ranges and correspond to the extreme abnormal lower and higher ranges, respectively.

Abnormal laboratory assessments deemed clinically significant by the investigator will be reported as an adverse event.

A listing of Participants with abnormal value(s) according to the following criteria will be summarized using Safety Analysis Set:

- Any laboratory value that falls into the pre-defined low or high panic ranges (L1 or H1) per the Q2 Laboratory Range Chart.
- Alanine aminotransferase (ALT) or aspartate aminotransferase (AST) \geq 3 × Upper Limit of Normal (ULN) and total bilirubin \geq 2 × ULN, inclusive (Hy's Law).
- AST or ALT \geq 5 × ULN,

- Creatinine $> 1.5 \times ULN$
- Participants positive for alcohol, urine drug screen or pregnancy assessments

All laboratory results, including pregnancy test, drug screen, and alcohol screen, will also be presented in subject data listings.

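### The SAP's Hy's Law listing criterion differs from the protocol's possible-Hy's-Law rule: it has no INR arm and no direct-bilirubin condition, which affects flagging and labelling in the study report

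*SAP*

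**What the plan says.** **SAP 10.3 (Laboratory Assessments)** plans a listing of participants with abnormal values in the Safety Analysis Set. Two of its criteria concern the liver:

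- ALT or AST ≥ 3 × ULN together with total bilirubin ≥ "2 × ULN, inclusive (Hy's Law");
- AST or ALT ≥ 5 × ULN.

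A further criterion is not specific to the liver: "Any laboratory value that falls into the pre-defined low or high panic ranges (L1 or H1) per the Q2 Laboratory Range Chart". The limits of those ranges are not given. No SAP criterion names INR or direct bilirubin.

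**Protocol Appendix 3, Table 6, footnote a** has two arms. The bilirubin arm needs ALT or AST ≥ 3 × ULN with total bilirubin at or above "2 × ULN (> 35% direct bilirubin) or ALT or AST"; the last words of that quote open the second arm, ALT or AST ≥ 3 × ULN with "INR > 1.5 which may indicate severe liver injury (possible Hy's Law), must be reported to the sponsor in an expedited manner".

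Both missing tests are collected. The chemistry panel in Table 6 contains "Total and direct bilirubin" and INR.

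**Protocol 5.2, Exclusion Criterion 6** states: "Participants with hyperbilirubinemia who have a history of Gilbert's syndrome may be eligible for the study".

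**The concern.** One name is attached to two different rules. The protocol's arms tell sites what to report urgently as possible Hy's Law. The SAP's bullet decides who carries that name in the study report, and it drops the word possible.

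A participant reported by a site under the protocol rule could then lack the matching flag in the SAP listing. Another participant could carry the label without ever having met the protocol's criterion. Anyone reconciling the listing with the expedited reports would have to explain each difference by hand. What is at stake is the clarity of a safety listing. No efficacy result, error rate or power figure depends on it.

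**Working it through.** The plan gives no figure to reproduce, so the check is a comparison of the two rules. I take all values as coming from one blood sample; neither rule says so.

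**Inputs**

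| Symbol | Condition | In protocol rule (Table 6, footnote a) | In SAP bullet (10.3) |
|---|---|---|---|
| A | ALT or AST ≥ 3 × ULN | yes | yes |
| B | total bilirubin ≥ 2 × ULN | yes, bilirubin arm | yes |
| D | direct share > 35% | yes, bilirubin arm | no |
| I | INR > 1.5 | yes, second arm | no |

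**Rules**

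- Protocol: A and [(B and D) or I].
- SAP: A and B.

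**Where they differ**

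1. *Protocol met, SAP bullet not met.* Given A, the SAP bullet fails only if B fails. Without B the protocol rule can be met only through I. The region is A, not B, I: ALT/AST ≥ 3 × ULN, total bilirubin < 2 × ULN, INR > 1.5. D plays no part.
2. *SAP bullet met, protocol not met.* A and B hold, so the protocol rule fails only if D and I both fail. The region is A, B, direct share ≤ 35%, INR ≤ 1.5.

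**Check by enumeration.** I crossed 6 ALT/AST values (1, 2.9, 3, 4.9, 5, 8 × ULN), 4 bilirubin values (1, 1.9, 2, 3 × ULN), 4 direct shares (10%, 35%, 36%, 60%) and 4 INR values (1.0, 1.5, 1.6, 2.5): 6 × 4 × 4 × 4 = 384 combinations.

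- Region 1: 4 × 2 × 4 × 2 = 64. Half of these (32) have ALT/AST < 5 × ULN, so the ≥ 5 × ULN criterion does not catch them either.
- Region 2: 4 × 2 × 2 × 2 = 32.
- Both rules met: 96. Neither met: 192. Total 64 + 32 + 96 + 192 = 384.

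These counts show only that both regions exist. They are not frequencies.

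**Two illustrations with assumed values**

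- ALT 4 × ULN, total bilirubin 1.2 × ULN, INR 1.8. Protocol: met, since 4 ≥ 3 and 1.8 > 1.5. SAP Hy's Law bullet: not met, since 1.2 < 2. SAP ≥ 5 × ULN criterion: not met, since 4 < 5. The alert-range criterion covers any laboratory value, so ALT or INR (or another test) could still put this participant in the listing. The documents do not let us say whether it would.
- ALT 3.1 × ULN, total bilirubin 2.2 × ULN, 15% direct, INR ≤ 1.5. SAP bullet: met, since 3.1 ≥ 3 and 2.2 ≥ 2. Protocol: not met, since 15% ≤ 35% and INR ≤ 1.5. Gilbert's syndrome with a transaminase rise would give this pattern.

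**The case against.** The strongest reply is that the two rules do different jobs. Footnote a is a trigger for reports from site to sponsor. Protocol 9.4.5 plans only descriptive laboratory summaries and no Hy's Law analysis, so the SAP was free to choose a screen. This stands in part. SAP 7.6 does record another change to a safety definition ("presyncope was removed in the formal definition of AEOSI in Section 10.2.1"), and a reader might infer that the liver rule is an undisclosed departure from a planned analysis. With no such analysis in the protocol, that inference is weak. What remains is the shared name.

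A second reply is that a wider rule is the safer error. That is right for the bilirubin part: dropping the direct-bilirubin condition only widens the screen and cannot miss anyone. It does not answer the INR part, where the SAP rule is narrower.

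A third reply is that nothing is really lost, and most of this stands. The SAP does not alter expedited reporting. All laboratory results are listed. Chemistry shift tables are planned at each post-baseline visit. A value that the investigator considers clinically significant becomes an adverse event. A reader might infer that protocol-defined cases would vanish from the report; the documents do not support that. What can be lost is one automatic flag.

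The Gilbert's route is also narrow. Raised bilirubin alone does not meet the SAP bullet. ALT/AST must also reach 3 × ULN, and Exclusion Criterion 6 names ALT or AST ≥ 2 × ULN among its excluding findings at entry.

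**Conclusion.** The point holds as a modest inconsistency in a safety listing. Unflagged protocol-defined cases arise only from the absent INR arm, when total bilirubin is below 2 × ULN. They escape every SAP liver criterion when ALT/AST is also below 5 × ULN, and then depend on unspecified alert limits. Labelling without the protocol rule being met arises only with a direct share of at most 35% and INR of at most 1.5.

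No frequency can be derived from the documents. A reader might infer that this touches the drug's most serious laboratory risk, or that the report's liver conclusion would contradict the expedited reports. Neither is supported. Protocol 2.3.1 reports no clinically important trends in safety laboratories, the adverse events of special interest contain no hepatic term, and one listing criterion does not determine a conclusion.

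The verdict rests on the two rules as written and on INR and direct bilirubin being measured as Table 6 sets out. It takes no view on which rule is clinically better.

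**What to change.** Reconcile SAP 10.3 with Protocol Appendix 3:

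- add the protocol's ALT or AST ≥ 3 × ULN with INR > 1.5 criterion to the abnormal-value listing;
- keep ALT or AST ≥ 3 × ULN with total bilirubin ≥ 2 × ULN, described as a broader biochemical screen and not as confirmed Hy's Law;
- show the direct-bilirubin share and INR for every flagged participant, so that those meeting the protocol's rule can be identified.

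The cost is a small change of text and programming on tests already in the chemistry panel. Nobody flagged by the present bullet is dropped. Separate Gilbert's flags, or counts and percentages by arm, would be a presentation choice and are not needed to resolve the mismatch.

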10.3.1. Laboratory Specific Derivation

Multiple of upper limit of normal (ULN) = result / ULN

10.3.2. Laboratory Normal Reference Ranges

Quantitative laboratory measurements will be compared with the relevant laboratory reference ranges in SI units and categorized as:

- L1: result less than the low alert (L1)
- Low: result within the low alert (L1) and lower limit of normal (LLN) (L1 and LLN limit included)
- Normal: result within the laboratory normal reference range (LLN and ULN limit included)
- High: result within the ULN and high alert (H1) (ULN and H1 limit included)
- H1: result greater than the high alert (H1)

10.4. Vital Signs

The following vital signs measurements will be reported for this study.

- Supine and standing systolic blood pressure (SBP), (millimeter of mercury [mmHg])
- Supine and standing diastolic blood pressure (DBP) (mmHg)
- Supine and standing pulse rate (beats per minutes [bpm])
- Sitting or supine respiratory rate (breaths/min)
- Body Temperature (°C)
- Weight (kg)
- Height (cm)
- BMI (kg/m2) [derived]

The orthostatic vital signs will be derived as the difference found by subtracting the supine measurement from the standing measurements. The orthostatic measurement will be summarized with the supine and standard measurements.

These vital signs (with the exception of the BMI which will be calculated programmatically) will be measured during the screening visit and each in-clinic scheduled visit. Height (cm) will be obtained at screening visit only.

The following summaries will be provided for vital signs data:

Jazz Pharmaceuticals

Statistical Analysis Plan - Protocol JZP385-201

- Observed and change from baseline by visit
- Incidence of markedly abnormal criteria by visit

10.4.1. Vital Signs Markedly Abnormal Criteria

Markedly abnormal quantitative vital signs measurements will be identified in accordance with the following predefined markedly abnormal criteria as specified in Table 6.

Table 6 Vital Signs Predefined Markedly Abnormal Criteria

Variable (unit)	Low	High	
SBP (mmHg)	\leq 90 mmHg AND change from baseline \leq -20 mmHg	≥ 180 mmHg AND change from baseline ≥ 20 mmHg	
DBP (mmHg)	≤ 50 mmHg AND change from ≤ -15 mmHg	≥ 110 mmHg AND change from baseline ≥ 15 mmHg	
Orthostatic SBP (mmHg)	\geq 20 mmHg drop with posture change from supine to standing		
Orthostatic DBP (mmHg)	≥ 10 mmHg drop with posture change from supine to standing		
Pulse rate (bpm)	≤ 50 bpm AND change from baseline ≤ -15 bpm	≥ 120 bpm AND change from baseline ≥ 15 bpm	
Orthostatic pulse rate≥ 30 bpm increase with posture change from supine to standing (bpm)			
Weight (kg)	percentage change from baseline ≤	percentage change from baseline ≥	
Temperature (°C)	-10.0% ≤ 35.0 °C	10.0 % ≥ 39.0 °C	

Note: bpm: Beats per minute. DBP: Diastolic Blood Pressure. kg: kilogram. mmHg: Millimeter of mercury. SBP: Systolic Blood Pressure

10.5. ECG

A standard 12-Lead ECG will be recorded with the subject resting in supine for at least 5 minutes. ECGs will be performed during the Screening visit, Baseline visit, in-clinic scheduled visit or early termination visit. Results from the central ECG core lab will be included in the reporting of this study. The following ECG parameters will be reported:

- PR Interval (msec)
- RR Interval (msec)

Jazz Pharmaceuticals

Statistical Analysis Plan - Protocol JZP385-201

- QRS Interval (msec)
- QT Interval (msec)
- QT Bazett's correction (QTcB) Interval (msec) [derived]
- QT Fridericia's correction (QTcF) Interval (msec) [derived]
- Mean HR (bpm)
- Overall assessment of ECG:
 - Normal
 - o Abnormal

The following summaries will be provided for ECG data across the study:

- Observed and change from baseline by visit (for quantitative measurements)
- ECG parameters results will be listed over time

10.5.1. ECG Abnormal Criteria

Abnormal quantitative ECG measurements will be identified in accordance with the following predefined markedly abnormal criteria:

Observed values for QT interval, QTcB interval and QTcF will be classified as follows at each time point:

- > 450 msec
- > 480 msec
- > 500 msec

Change from baseline for OT interval, OTcB interval and OTcF will be classified as follows:

- >30 msec increase from baseline
- >60 msec increase from baseline

A listing of participants meeting markedly abnormal criteria as well as a listing of participants with abnormal ECG overall assessment will also be provided based on the Safety Analysis Set.

10.6. Other Safety Endpoints

10.6.1. Columbia-Suicide Severity Rating Scale

The Screening/Baseline version of the C-SSRS will be administered to participants at screening visit.

The Since Last Visit version of the C-SSRS will be administered to participants at every scheduled in-clinic after the screening visit 2 up to the Safety Follow-up visit or early discontinuation visit.

The following summaries will be provided for the C-SSRS data by visit and by treatment group:

- Number and percentage of participants with any suicidal ideation (i.e., having responded yes to any of the 5 types of suicide ideation) as well as broken down by type of suicidal ideation
- Number and percentage of participants with any suicidal behavior (i.e., having responded yes to any of the 4 or 5 types of suicidal behavior, as applicable) as well as broken down by type of suicidal behavior
- Number and percentage of participants with any suicidal behavior or any suicidal ideation;
 a subject having reported both suicidal behavior and suicidal ideation will be counted only once
- Number and percentage of participants with self-injurious behavior without suicidal intent

Missing data will not be imputed. All C-SSRS parameters will be presented in the subject data listing.

10.6.2. Safety and COVID-19 Considerations

10.6.2.1. Alternative methods for safety assessments

For remote visits, the Investigator will remain in contact with the subject via telephone to discuss adverse events, as well as to evaluate efficacy and tolerability of the prescribed dose of study intervention. Note that all protocol deviations due to changes in how assessments are collected will be recorded and labeled as related to COVID-19 mitigations.

10.6.2.2. Assessment of safety due to COVID-19 considerations

Safety summaries will combine data that is collected on-site and remotely (e.g., exposure, adverse event, and CSSR-S). A total number of assessments not done due to COVID-19 restrictions will be provided. A summary table of all protocol deviations relating to COVID-19 restrictions will be included.

11. PHARMACOKINETIC ANALYSES

The dosing regimen during the PK evaluation will be the subject's currently assigned treatment regimen. Participants will take their dose at similar conditions to those normally followed at home. Blood samples will be collected at 0 (pre-dose), and 1 sample between 0.5 to 3 hours post-dose for Weeks 1, 4 and 12 visits; and pre-dose, 1 sample between 0.5 to 3 hours postdose, and 1 sample anytime between 5 to 8 hours postdose for Week 8 visit. In the event a shorter clinic visit is needed because of the COVID-19 pandemic, the 5 to 8 hour postdose sample at W8 may be omitted with approval from the Sponsor's Medical Monitor.

11.1. Pharmacokinetic Concentrations

The plasma concentrations data for each analyte will be listed by participant and listing will include visit, nominal timepoint, and actual time postdose.

The plasma concentration data will be used as part of population PK and population exposureresponse analysis that will be described in separate SAP(s) and its results will be presented separately from the study data.

The plasma concentration data will be used as part of population PK and population exposureresponse analysis that will be described in separate SAP(s) and will be presented separately from the study data.

